- Outcomes: The primary study outcome is reduction of clinical activity of TED, as determined by both the CAS and VISA scores. We will use both scales because there is currently disagreement as to which scale serves as a better overall assessment tool. Secondary outcome measures will include reduction of specific aspects of TED, including proptosis, diplopia, and eyelid retraction, as well as a validated TED-specific quality of life survey. These elements are captured in part by the 2 scales but also will be evaluated separately. Comparison of our primary and secondary outcomes between the treatment and control groups and with published studies of steroid treatment for TED may provide us with an indication of the relative efficacy of celecoxib treatment and whether further study is warranted. Treatment safety also will be assessed, and adverse events recorded. A recent prospective study of intravenous corticosteroid dosing for TED reported major adverse events in 10/159 (6.3%) of subjects and minor adverse events such as gastric distress, mild BP increase not requiring medication, and local skin reactions in about 25% of subjects. We anticipate a lesser incidence of minor or major adverse events based on the side effect profile of celecoxib in patients without co-morbidities placing them at higher risk (most TED patients are young and otherwise healthy). Occurrence of adverse events at a rate

greater than what has been reported for intravenous corticosteroid (an accepted method of TED treatment) would suggest that risk of celecoxib treatment exceeds any benefit.

- Biospecimens will be collected in this study, to include urine for a pregnancy test for female patients of childbearing age to determine eligibility, as well as blood as noted above that will be drawn by the clinical lab.
- Study length: Subjects will be followed for 12 months.
- Safety monitoring: As noted, baseline blood testing and phone surveillance will be performed. If abnormal results are found during drug treatment, then subjects will be advised to stop the medication and will be examined by the PI or other MD investigator. Adverse events will be reported to the IRB per institutional policy.
- Subjects may be taken out of the study if:
 - Staying in the study would be harmful.
 - Treatment required is not allowed in the study.
 - Those that fail to follow instructions.
 - Subjects become pregnant.
 - The study is cancelled.

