 - There may be other reasons to take subjects out of the study that we do not know at this time.

5. Inclusion/Exclusion Criteria

Eligibility criteria:

- *Recent diagnosis of thyroid eye disease (within the past 6 months)*
- Have ocular symptoms or signs of TED with a CAS score of at least 3
- Ages 18-80 years

Exclusion criteria:

- Pregnancy
- Previous treatment with corticosteroid for TED for >2wks
- Previous treatment with orbital radiation for TED
- Impaired renal function
- Impaired hepatic function
- *Treatment with antihypertensive medications except beta-blockers*
- History of congestive heart failure, cardiac valvular disease, or coronary artery disease
- Allergy to NSAID or previous adverse reaction (ie. GI bleeding)
- Vision loss due to compressive optic neuropathy

Target 40 participants will be enrolled in this study.

6. Drugs/ Substances/ Devices

Celecoxib (Celebrex) is a non-steroidal anti-inflammatory drug approved by the Food and Drug Administration (FDA) for the treatment of pain, osteoarthritis, rheumatoid arthritis, and ankylosing spondylitis. We will be using the recommended dosage of 100 mg twice a day over the course of 3 months. Celecoxib for TED is an off-label usage.

7. Study Statistics

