The primary study outcome is reduction of clinical activity of TED, as determined by both the CAS and VISA scores. We will use both scales because there is currently disagreement as to which scale serves as a better overall assessment tool. Secondary outcome measures will include reduction of specific aspects of TED, including proptosis, diplopia, and eyelid retraction. These elements are captured in part by the 2 scales but also will be evaluated separately. Change in quality of life will be measured by a validated questionnaire as another secondary outcome measure. Comparison of our primary outcomes between treatment and control groups will provide us with an indication of the relative efficacy of celecoxib treatment. Treatment safety also will be assessed, and adverse events recorded. A recent prospective study of intravenous corticosteroid dosing for TRO reported major adverse events in 10/159 (6.3%) of subjects and minor adverse events such as gastric distress, mild BP increase not requiring medication, and local skin reactions in about 25% of subjects. We anticipate a lesser incidence of minor or major adverse events based on the side effect profile of celecoxib in patients without co-morbidities placing them at higher risk (most TED patients are young and otherwise healthy). Occurrence of adverse events at a rate greater than what has been reported for intravenous corticosteroid (an accepted method of TED treatment) would suggest that risk of celecoxib treatment exceeds any benefit. Observation of adverse events in excess of this rate during the treatment phase would require review, and consideration of early study termination. The changes in either the CAS or VISA score will be compared between the celecoxib and observation groups to determine whether a trend or significant difference can be found.

8. Risks

The study procedures, apart from the proposed treatment, carry no risk beyond that of standard clinical care. Celecoxib has well-described risks especially in certain patient populations, who will be excluded from this study as noted. Below is an enumeration of risks copied from the package insert:

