- **Cardiovascular warning:** All prescription NSAIDs, like CELEBREX, ibuprofen, naproxen, and meloxicam have the same cardiovascular warning. They may all increase the chance of heart attack or stroke that can lead to death. This chance increases if you have heart disease or risk factors for it, such as high blood pressure or when NSAIDs are taken for long periods. Congestive heart failure and peripheral edema has also occurred in some patients has also been noted.
- CELEBREX should not be used right before or after certain heart surgeries.
- Stomach and intestine risk: All prescription NSAIDs have the same warning for serious stomach and intestine problems: They may cause ulcers and bleeding, which can occur without warning and may cause death.
- **Renal warning:** Long term use of NSAIDs, like CELEBREX, have resulted in renal papillary necrosis. Patients at risk are those with impaired renal function, heart failure, liver dysfunction, those taking diuretics, ACE inhibitors, and angiotension II inhibitors.

Date: January 21, 2017 Principal Investigator: [name] Application Number: IRB00094787

• Serious skin and allergic reactions can occur with CELEBREX. CELEBREX shold not be taken if one has had an asthma attack, hives, or other allergies to aspirin, other NSAIDs, or certain drugs called sulfonamides.

Risks of corticosteroid treatment are noted in section 7 with at least 25% of patients experiencing a minor or major adverse event. Orbital radiotherapy carries theoretic risk of ocular radiation toxicity (cataract formation, radiation retinopathy or optic neuropathy) and second malignancy occurrence, but the actual rate of such events is not known. Untreated, some patients with TED may have spontaneous improvement while others will progress to more severe manifestations. Increased disease activity at presentation is a predictor for progression, and we thus are including only subjects with clinical activity that may put them at risk for such changes. Treatment is effective only during the active phase of TED, and observation may result in irreversible proptosis or strabismus requiring subsequent surgery.

9. Benefits

The major benefit of the study is anticipated to be reduction of TED severity as measured by clinical activity assessment.

10. Payment and Remuneration

Subjects will not be compensated for participation.

11. Costs

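### No blood pressure reading is required before or during celecoxib, although Section 8 names high blood pressure as a risk factor on NSAIDs; readings at three existing visits would close the gap cheaply

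*Combined protocol and SAP*

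**What the plan says.** **Monitoring (Section 4, Study Procedures).** Subjects have a medical history and an eye examination, with visits at baseline and at months 1, 3, 6 and 12. The celecoxib arm has blood counts and renal and hepatic tests at baseline, 1 month and 3 months. Physicians on the study team telephone subjects monthly and ask about swelling, blood in the urine, skin changes and exercise tolerance. Women of childbearing age have a urine pregnancy test. The safety monitoring paragraph reads: "As noted, baseline blood testing and phone surveillance will be performed". The rule for acting on what is found follows in the same paragraph: "If abnormal results are found during drug treatment, then subjects will be advised to stop the medication".

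**Eligibility (Section 5).** The only criterion that bears on hypertension is the exclusion for "Treatment with antihypertensive medications except beta-blockers". Heart failure, valvular disease and coronary disease are excluded separately. The age range is 18 to 80 years.

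**Risks (Section 8).** The section says that the populations at particular risk from celecoxib are excluded. On heart attack and stroke with NSAIDs it states: "This chance increases if you have heart disease or risk factors for it, such as high blood pressure". Its renal warning covers, among others, "those taking diuretics, ACE inhibitors, and angiotension II inhibitors".

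**Benchmark (Sections 4 and 7).** Adverse events on celecoxib are to be judged against a study of intravenous corticosteroids. The milder events in that study are given as "minor adverse events such as gastric distress, mild BP increase not requiring medication, and local skin reactions in about 25% of subjects". For the serious ones, the plan says that the study "reported major adverse events in 10/159 (6.3%) of subjects". Section 7 then states how the benchmark is used: "Observation of adverse events in excess of this rate during the treatment phase would require review, and consideration of early study termination".

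**The concern.** The plan gives an NSAID off-label for 3 months and cites a warning that high blood pressure makes its most serious listed harms more likely. It then asks for no measurement that would show whether a subject has high blood pressure. Section 8 relies on exclusions to keep higher-risk subjects out, and for blood pressure the Section 5 exclusion does only part of that work.

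Two things are at stake. The first is subject safety: someone with untreated hypertension can be randomised and start celecoxib in full compliance with the protocol. The second is the safety comparison: one kind of event counted in the benchmark has no planned means of detection in this trial. The first matters more and is better supported by the documents.

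**Working it through.** This is a question of what the plan requires, so most of the check consists of setting its sections side by side.

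**1. The plan's own figure.** Major events in the steroid study: 10/159 = 0.0629, or 6.3%, as stated. The figure that involves blood pressure is the other one, the minor-event rate of about 25%. The documents do not say how much of that 25% was blood pressure.

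**2. What each required procedure can show about blood pressure.**

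| Procedure | Arm | What it can show |
|---|---|---|
| Medical history and medication list | both | a known diagnosis or current treatment |
| Eye examination | both | no blood pressure reading is specified |
| Blood tests at baseline, 1 and 3 months | celecoxib | renal and hepatic function and blood counts |
| Monthly phone interview | not restated by arm | symptoms; a symptom-free rise would be missed |
| Urine pregnancy test | women of childbearing age | not relevant |

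The plan does not forbid a routine clinic reading, and a rise found that way could be recorded. It does not require one.

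**3. What happens to each kind of hypertensive subject at entry.**

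- *Treated with a drug other than a beta-blocker:* excluded by Section 5.
- *Treated with a beta-blocker alone:* eligible. This exemption fits the Section 8 renal warning, which does not name beta-blockers, and it is not criticised here.
- *Diagnosed but untreated:* the history would be expected to reveal it, but no criterion then excludes the subject.
- *Undiagnosed:* the history cannot reveal it, so only a reading would.

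The last two groups carry the risk factor that Section 8 names, and both may start celecoxib.

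**4. During treatment.** The advice to stop the drug depends on an abnormal result. If no reading is taken, a symptom-free rise gives no result, so nothing prompts the advice.

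**5. Benchmark against monitoring.** The steroid rate includes mild rises that needed no medication. By their nature these are found by measuring. The required procedures on celecoxib include no such measurement, so this component of the comparison is not looked for.

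**6. Workload of the remedy.** Three existing visits (baseline, 1 month, 3 months) × 40 subjects = 120 readings if everyone attends. At an assumed 3 to 5 minutes each, 120 × 3 = 360 minutes and 120 × 5 = 600 minutes, so 6 to 10 hours over the whole trial, before repeat readings. Adding the 6 and 12 month visits would make 5 × 40 = 200 readings.

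**The case against.** The strongest reply is that the plan already has several partial safeguards. It takes a history of health conditions, excludes most patients on antihypertensive drugs, excludes overt heart disease, describes most patients with this condition as young and otherwise healthy, and lets the investigators withdraw anyone for whom staying in would be harmful. These points stand, and they narrow the gap. They do not close it: undiagnosed hypertension passes all of them, known untreated hypertension meets no exclusion criterion, and eligibility runs to age 80.

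A second reply is that Section 8 presents high blood pressure as a pre-existing risk factor. It does not list a rise in blood pressure as an effect of celecoxib, and the only rise mentioned in the documents is on corticosteroids. That is correct. It makes the case for a baseline reading stronger than the case for readings on treatment. The latter rest on the benchmark, which counts such events, and on the stop rule, which needs a result to act on.

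A third reply is that a stop rule based on one office reading could end treatment needlessly in a small arm and weaken the efficacy comparison. This also stands, and is why the remedy needs a stated limit and a repeat reading.

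A reader might go further and infer that the safety comparison is biased in favour of celecoxib, or that missed rises would keep the trial below its review trigger. The documents do not support either inference. They do not give the blood pressure share of the steroid events or say how that study found its events. The monthly questioning on celecoxib may raise the recorded rate. The plan does not say which benchmark rate sets the trigger, and mild rises would have no bearing on the 6.3% major-event rate.

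**Conclusion.** The point holds as a safety improvement that should be made. The plan leaves a risk factor it names itself without a required measurement, both at entry and during treatment. This follows from the text and needs no numerical assumption.

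Its consequences cannot be sized. The documents give no basis for estimating how many of the 40 subjects would have untreated hypertension or how often blood pressure would rise on celecoxib. For the adverse event comparison, it can be said only that one component of the benchmark is not looked for; neither the size nor the net direction of any effect can be established. No primary or secondary efficacy outcome is affected, and the point does not show that any subject would be harmed. The recommendation rests on the low cost of a reading set against a serious, named risk.

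**What to change.** Add to Section 4: measure and record blood pressure at baseline before the first dose, and at the existing 1 and 3 month visits, in both arms, and report increases as adverse events. The observation arm then gives a concurrent reference for blood pressure, which the external steroid figure cannot. Readings at 6 and 12 months are optional.

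Set in advance, with the IRB, a blood pressure limit that must be confirmed by a repeat reading. A subject above it at baseline does not start celecoxib; a subject above it on treatment is advised to stop under the existing Section 4 rule. It is best to take the baseline reading before randomisation, so that the limit works as an eligibility criterion and applies to both arms alike.

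The cost is the workload worked out above plus some repeat readings and follow-up of raised values, with no new visits. Other downsides are a possibly higher recorded adverse event rate, a few fewer eligible subjects and a few treatment discontinuations. The discontinuations matter in an arm of about 20 (assuming equal allocation, which the plan does not state), and the repeat reading is there to limit them.

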- In addition to cytokines, activated T-cells produce ligands for peroxisome proliferator activated receptor (PPAR) gamma. These ligands include prostaglandins created via the cyclooxeganse-2 (COX-2) pathway. PPAR-gamma activation has been implicated in systemic adipogenesis in patients taking thiazolidinedione drugs for glycemic control, and *in vitro* studies of cultured orbital fibroblasts have shown that exposing cells to PPAR-gamma ligands such as specific prostaglandin analogues results in transformation of fibroblasts into adipocytes. This effect is more robust with TED fibroblasts than in cells isolated from control patients. Inhibiting the PPAR-gamma pathway *in vitro* with a selective COX-2 inhibitor blocks fibroblast transformation. A single case report in the literature also supports the possible *in vivo* efficacy of COX-2 inhibition in active TED.
- Based on these *in vitro* and *in vivo* findings, we propose to treat a cohort of patients with active TED using a selective COX-2 inhibitor, celecoxib (Celebrex), and to compare these patients to an observational control group. We hypothesize that celecoxib will reduce the severity of disease and/or prevent progression to proptosis, diplopia, and corneal exposure or compressive optic neuropathy. We will assess the effect of the treatment using validated clinical scoring tools, including the Clinical Activity Scale (CAS) from the European Graves Orbitopathy Group (EUGOGO) and the VISA (vision, inflammation, strabismus, appearance) scale of the International Thyroid Eye Disease Study (ITEDS) group. We will also use a validated Graves ophthalmopathy quality of life survey as a secondary outcome measure. Outcomes will be assessed at timepoints noted below with a 3-month period of treatment and follow-up for 1 year.

4. Study Procedures

- Patients will be recruited from the Wilmer Eye Institute practices of the investigators.
- The exam will include a thorough history including a list a medications, health conditions previous surgeries and medical allergies (standard of care).
- The complete eye examination will measure visual acuity, eye movements (sensorimotor exam), visual fields, proptosis, pupil function, anterior segment evaluation, and lastly dilated fundus

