exam to evaluate the potential subject's optic nerve. Photographs (external, eye movements, optic nerve) may be taken as needed. This eye examination is standard of care on any thyroid eye disease patient. Findings from the eye exam will be used to determine a CAS and VISA score. The CAS takes into account 7 manifestations (spontaneous retrobulbar pain, pain with eye movement, eyelid erythema, eyelid edema, conjunctival injection, chemosis, and caruncular swelling) with 1 point assigned for each positive finding. The VISA score ranges from 0-16 based on findings related to inflammation, strabismus, and eyelid changes and proptosis (appearance). Both scales were developed to assess features of active disease that might change with treatment.

- Study subjects will be randomly assigned to observation with no prescription treatment, or treatment with oral celecoxib 100 mg twice daily for 3 months. Patients will have a full clinical exam at baseline, 1 month, 3 months, 6 months, and 12 months, with additional clinical visits more frequently if indicated by disease course/activity. The proposed frequency of clinic visits is within standard of care for newly diagnosed active-phase TED.
- For those subjects randomized to the treatment group, baseline blood testing for blood counts, renal and hepatic function (BUN, Cr, AST, ALT, total bilirubin) will be obtained prior to starting the drug. Testing will be performed by a standard clinical laboratory and billed to insurance. Testing will be repeated at 1mo and 3mo after randomization/initiation of therapy for those receiving celecoxib. Abnormal BUN or creatinine (outside normal range) on lab testing or any previous/current kidney disease will be the criteria for labeling a patient as having impaired renal function. Abnormal liver enzymes (AST, ALT, bilirubin outside normal range) or previous/current liver disease will determine whether a patient is labeled as having impaired hepatic function. Monthly phone interviews also will be conducted by physician study team members to determine if other side effects, such as edema, may be occurring. Subjects will be asked specifically about peripheral swelling, any blood in urine or skin discoloration, or changes in exercise tolerance. Positive responses will trigger an unscheduled visit with the PI or co-investigator MD. Patients will be cautioned not to take additional NSAID medications while on Celecoxib, as this may increase the chance for adverse effects.

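### Section 5 does not exclude patients allergic to certain sulfonamides, although Section 8 says they should not take celecoxib

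*Combined protocol and SAP*

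**What the plan says.** Section 5 has one allergy item among its exclusions: "Allergy to NSAID or previous adverse reaction (ie. GI bleeding").

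Section 8 opens with a general assurance: "Celecoxib has well-described risks especially in certain patient populations, who will be excluded from this study as noted". It then lists warnings from the package insert. The allergy warning begins "Serious skin and allergic reactions can occur with CELEBREX" and continues that the drug "shold not be taken if one has had an asthma attack, hives, or other allergies to aspirin, other NSAIDs, or certain drugs called sulfonamides". The renal warning in the same list reads "Patients at risk are those with impaired renal function, heart failure, liver dysfunction, those taking diuretics, ACE inhibitors, and angiotension II inhibitors".

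Section 4 (Study Procedures) describes the history taken at the examination: "The exam will include a thorough history including a list a medications, health conditions previous surgeries and medical allergies (standard of care"). It gives the allocation as follows: "Study subjects will be randomly assigned to observation with no prescription treatment, or treatment with oral celecoxib 100 mg twice daily for 3 months".

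**The concern.** Section 8 states who should not take the study drug. Section 5 decides who may be randomised to it. For allergy the two do not match: the Section 8 warning extends to certain sulfonamides, and the Section 5 item stops at NSAIDs.

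What is at stake is mainly patient safety. The entry rule admits a group that the protocol's own risk section says should not receive the drug, in a warning about serious skin and allergic reactions.

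There is also a smaller consequence for the comparison. If the allergy is acted on only after randomisation, it affects only patients allocated to celecoxib, because the observation group receives no study drug. Any resulting losses would fall on one side.

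**Working it through.** No figure in the plan needs reproducing. The check sets the Section 5 list against the Section 8 warnings and then looks for any other rule that would close the gap.

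**The nine exclusions in Section 5**

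1. Pregnancy
2. Corticosteroid for TED for more than 2 weeks
3. Orbital radiation for TED
4. Impaired renal function
5. Impaired hepatic function
6. Antihypertensive drugs other than beta-blockers
7. Heart failure, valvular disease or coronary disease
8. NSAID allergy or previous adverse reaction
9. Vision loss from compressive optic neuropathy

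Number that name sulfonamides: 0 of 9. The word occurs only in Section 8.

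**Section 8 allergy warning against Section 5**

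| Trigger in Section 8 | Matching exclusion |
|---|---|
| Aspirin | 8 (aspirin is an NSAID) |
| Other NSAIDs | 8 |
| Certain sulfonamides | none |

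Covered: 2 of 3.

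**Section 8 renal warning against Section 5, for comparison**

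| At-risk group in Section 8 | Matching exclusion |
|---|---|
| Impaired renal function | 4 |
| Heart failure | 7 |
| Liver dysfunction | 5 |
| Diuretics | 6 |
| ACE inhibitors | 6 |
| Angiotensin II inhibitors | 6 |

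Covered: 6 of 6, if the last three drug classes are read as falling under "Treatment with antihypertensive medications except beta-blockers". That reading is an assumption.

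**Exposure of a patient admitted through the gap and allocated to celecoxib**

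2 × 100 mg = 200 mg a day for 3 months.

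**Other provisions that might close the gap**

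- *Allergy history (Section 4).* It is taken, but nothing links a sulfonamide entry to ineligibility.
- *Laboratory tests (Section 4).* They cover blood counts and renal and hepatic function. They do not detect a past allergy.
- *Monthly calls (Section 4).* They take place during treatment, so they can detect harm but cannot prevent exposure. The topics listed are swelling, blood in the urine, skin discoloration and exercise tolerance; hives and asthma are not among them.
- *Removal when continued participation would be harmful (Section 4).* This is discretionary, applies after enrolment and does not mention allergy.

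None of these is an entry criterion.

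**Weight of one-sided losses**

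The target is 40 participants, so each is 1/40 = 2.5% of the trial. The allocation ratio is not stated. If it were 1:1 (an assumption), the celecoxib group would have 40/2 = 20 patients, and each would be 1/20 = 5% of it.

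**The case against.** The missing wording is not in dispute. The strongest case on the other side concerns how much it matters.

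- *The assurance that opens Section 8 may be narrower than it looks.* It speaks of certain populations and may mean only those listed in Section 5. That reading is possible, and on it the assurance is not contradicted. The mismatch between the allergy warning and the exclusion remains, because it does not depend on that sentence.
- *The renal comparison is selective.* Section 8 also mentions high blood pressure and the time around certain heart surgeries. Section 5 excludes most antihypertensive treatment but not hypertension itself, and it names no heart surgery. This is fair: the 6 of 6 does not show that Section 5 mirrors Section 8 everywhere. It shows only that one neighbouring warning was carried over and this one was not fully carried over.
- *The adverse-reaction wording might cover any drug.* It has no stated object, but it follows NSAID allergy and its example is GI bleeding. The natural reading is a reaction to an NSAID. A bar on anyone who ever reacted to any drug would be implausibly broad.
- *Physicians would have to record the allergy and then disregard their own protocol.* This stands as mitigation. It makes dosing less likely, and the removal rule adds to that. It does not make the patient ineligible. The consent pages are not available; a warning there would not be an entry criterion either.
- *The amendment takes more than one line of thought.* This is partly right. The documents do not say which sulfonamides are meant, so the sponsor must go back to the package insert it copied from.

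**Conclusion.** The concern holds. As written, Section 5 admits patients whom Section 8 says should not take celecoxib, namely those with an allergic reaction to certain sulfonamides and no NSAID allergy or reaction. Confidence in the mismatch is high. It rests on one reading, that the adverse-reaction wording refers to NSAIDs.

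The counts above describe coverage of wording, not risk. The number of such candidates and the chance of a reaction cannot be derived from the documents, and no claim is made that dosing is likely.

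The point should be fixed: it is a safety mismatch within the protocol, partly mitigated by ordinary clinical care and cheap to close. It does not affect the endpoints, the planned comparison or the target of 40.

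**What to change.** Widen the Section 5 allergy item so that it covers the whole Section 8 warning. For example: *any past allergic-type reaction, including asthma or hives, to aspirin, to another NSAID or to a listed sulfonamide; or a previous NSAID adverse reaction such as GI bleeding*. Add the list of sulfonamides, taken from the package insert.

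Apply the item to every candidate before randomisation, using the allergy history already taken, so that affected patients are not removed from the celecoxib group alone.

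The cost is a short amendment to Section 5 and the work of settling the list. No new test or data collection is needed. Some candidates will become ineligible; the documents do not show how many.
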